Participants and Recruitment. Potential participants will be identified automatically using VUMC's *Subject Locator* to query the EHR for patients with upcoming clinic appointments who meet the discrete inclusion and exclusion criteria. In addition, VUMC population health and quality improvement initiatives have created a report that identifies established patients with diabetes who receive care at the primary care clinics participating in the study and have current diabetes care gaps (e.g., no diabetes eye exam in the last year). These patients are the target population for study (i.e., Vanderbilt primary care patients with diabetes) and as such these patients are potentially eligible to participate in the study. With approval of the clinic director, we will send potentially eligible patients a recruitment letter describing the study and providing them with the contact information (study phone number and e-mail address) for IRB-approved study personnel. If after receiving the letter, a patient is interested in the study, they may contact study personnel to learn more and consider participating in the study. The recruitment letter will also include a QR code and URL link to a REDCap site where interested patients can review eligibility criteria, review the consent form, and enroll. Within each step of this REDCap process, we have emphasized (i.e., underlined) statements encouraging potential participants to call or email study staff with any questions or concerns at any time and provide the study's phone number and e-mail address. For self-initiated consent, the study contact information is provided (email and phone) for prospective participants to contact trained study personnel with questions, prior to consent. Trained key study personnel will also contact patients after receiving the completed REDCap informed consent document to provide another opportunity to ask questions, confirm eligibility, and onboard the patient to the study. Patients who do not respond to the recruitment letter may be contacted by phone to ensure they received the letter and offer them information about the study.

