Participants will complete an electronic consent form and enroll online via Research Electronic Data Capture (REDCap™) version 5.0.8. Our target enrollment is 500 participants. Given the high prevalence of type 2 diabetes mellitus (T2DM) among racial and ethnic minority groups, it is important to ensure that these groups can benefit from digital health interventions. Therefore, we will ensure fair representation of minorities in the proposed research. Racial and ethnic minorities account for approximately 40% of patients with diabetes in the United States. We will use purposive sampling and over sampling as needed to help ensure our study sample is representative of the population as whole.

[Intervention.](#) The intervention involves the addition of a new feature to the Vanderbilt patient portal that will allow patients to use the My Health at Vanderbilt (MHAV) app on their mobile device (smartphone or tablet) to: (1) receive notifications when they are due for certain types of diabetes monitoring and preventative care and (2) initiate an order for the care. Automated notifications will be sent to patients if, according to the Health Maintenance section of their electronic health record and medical guidelines, they are due for a hemoglobin A1C blood test, microalbumin (kidney) urine test, diabetes eye exam, and/or pneumonia vaccine. If a patient receives a notification, the patient can initiate an order for the care using the MHAV app. After the patient initiates the order, the study team will process the order. Each weekday, the study team will use Epic's reporting workbench to identify patients that initiated orders and use the EHR's batch order functionality to generate the actual order for the patient's care (e.g., HgbA1c lab test). The patient will receive confirmation when the order has been processed and instructions to proceed to a Vanderbilt clinic or lab to receive the care. The patient's primary care physician will be the authorizing provider and once the patient receives the care, their primary care doctor will receive any results. If the patient has already received the care outside of Vanderbilt, the patient will be able to indicate this. For example, if according to the patient's Vanderbilt medical record they are due for a diabetes eye exam, the patient will receive a notification; however if they recently had a diabetes eye exam with an eye doctor outside of Vanderbilt, they will be able to report this using the same new MHAV feature.

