**Table 2: Outcomes and Measures**

Primary Outcome	Measures	Variable Type	How Collected	Time Point
Number of Diabetes Care Gaps through 12 Months	Number of diabetes care gaps per patient out of four possible: 
 
no diabetes eye exam in the last 12 months,
 
no hemoglobin A1C blood test in the last 6 months,
 
no urine microalbumin in the last 12 months, and
 
no pneumococcal vaccination of any kind (i.e., never received PPSV-23, PCV-13, PCV-15, or PCV-20)
 
	Ordinal	EHR abstraction	T 0 - T 3
Secondary Outcomes				
Number of Diabetes Care Gaps at 6 Months	Number of diabetes care gaps per patient out of four possible: 
 
no diabetes eye exam in the last 12 months,
 
no hemoglobin A1C blood test in the last 6 months,
 
no urine microalbumin in the last 12 months, and
 
no pneumococcal vaccination of any kind (i.e., never received PPSV-23, PCV-13, PCV-15, or PCV-20)
 
	Ordinal	EHR abstraction	T 0 - T 3
Attitudes toward Managing Diabetes in General	Items adapted from the Manage Disease in General Scale of the Chronic Disease Self-Efficacy Scales.	Continuous	Questionnaire	T 0 - T 3
Diabetes self-efficacy	Perceived Diabetes Self-Management Scale (PDSMS)	Continuous	Questionnaire	T 0 - T 3
Understanding of Diabetes Monitoring and Preventative Care	Unique study specific items to assess participants' understanding of recommended diabetes monitoring and preventative care	Categorical	Questionnaire	T 0 - T 2
Diabetes distress	Problem Areas in Diabetes Scale (PAID-5)	Continuous	Questionnaire	T 0 - T 3
Satisfaction with MHAV	System Usability Scale and user experience questions	Continuous	Questionnaire	T 0 - T 3
Patient-initiated orders	# of patient-initiated orders for evidence-based diabetes monitoring & preventative services (e.g., A1c)	Continuous	EHR Abstraction, Tableau & Clarity Servers	T 0 - T 3

Reported completion outside VUMC system	# of reports diabetes eye exams outside the VUMC system in response to the To-Do item received via the intervention  # of reports of outside diabetes eye exam that meet criteria for screening for diabetic eye disease.	Continuous	EHR Abstraction, Tableau & Clarity Servers	T 0 - T 3

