Blood glucose control	Hemoglobin A1C	Continuous	EHR abstraction	T 0 - T 3
Treatment intensification	Addition of: a. antihyperglycemic medications b. antihypertensive medications	Categorical	EHR abstraction	T 0 - T 3

T0 = baseline, T1 = 3-month follow-up, T2 = 6-month follow-up, and T3 = 12-month follow-up

Secondary intermediate outcomes include attitudes toward managing diabetes in general, diabetes self-efficacy, understanding of diabetes monitoring and preventative care, diabetes distress, satisfaction with MHAV, patient-initiated orders, and reported completion outside VUMC system. Additional secondary outcomes, blood glucose control and treatment intensification, will also be assessed by EHR abstraction.

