## 6.0 Statistical Analysis Plan

We will use descriptive statistics to characterize the study participants and the primary and secondary outcomes. For the primary analysis, an ordinal mixed effects regression model will be used. For dichotomous outcomes, a logistic mixed effects regression model will be used. For continuous outcomes, a multivariate mixed effects regression model will be used. If there is imbalance, we will control for baseline patient level covariates, including socioeconomic status, marital status, race/ethnicity, education level, age, sex, health literacy, technology use, and diabetes distress. We will allow for nonlinear associations by modeling continuous covariate with restricted cubic splines when needed. Similar models will be used for all the secondary outcomes except for HbA1c. Due to the frequency of HbA1c measurements, we will use a linear regression model as opposed to a mixed effects model with the HbA1c value at the 12-month timepoint as the dependent variable. Appropriate statistical methods, such as multiple imputation, will be used where missing data are present.

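### HbA1c is analysed from one 12-month value with no window, selection rule or baseline HbA1c, although a mixed model on the dated EHR values is available at little cost

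*Combined protocol and SAP*

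**What the plan says.** Section 6.0 uses mixed-effects models for the primary and secondary outcomes and makes one exception: "Due to the frequency of HbA1c measurements, we will use a linear regression model as opposed to a mixed effects model". The outcome in that regression is one measurement per person, the one taken at 12 months. The frequency of measurement is the only reason given.

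Table 2 lists HbA1c as a continuous secondary outcome over T0 to T3. The text after it says that "blood glucose control and treatment intensification, will also be assessed by EHR abstraction". Nothing in section 5.0 schedules a study HbA1c draw, sets a window around 12 months, or says which EHR value counts.

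Three other statements bear on the point:

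- In Table 2 one of the four care gaps is "no hemoglobin A1C blood test in the last 6 months", so the plan expects some participants to lack a recent value.
- Under the intervention (section 5.0), participants in that arm are notified when "they are due for a hemoglobin A1C blood test, microalbumin (kidney) urine test, diabetes eye exam, and/or pneumonia vaccine", so the intervention itself prompts HbA1c testing.
- Section 6.0 adds: "If there is imbalance, we will control for baseline patient level covariates". The list that follows does not contain baseline HbA1c. On missing data it says: "Appropriate statistical methods, such as multiple imputation, will be used where missing data are present". No imputation variables are named.

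**The concern.** A mixed model accepts any number of values per person on their actual dates, so the stated reason does not lead to the stated choice. Irregular testing is a problem for the single-value analysis. Under the plan's own 6-month standard, a fully up-to-date participant's last test may fall anywhere in months 6 to 12. A narrow window then leaves people without an observed outcome, and a wide one labels values drawn months apart as 12-month values. Because the window is unstated, the estimate and its precision depend on a choice that could be made after the data are seen.

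As written, earlier follow-up values do not enter the model as outcomes. Baseline HbA1c, usually the strongest predictor of later HbA1c, is not named as a covariate.

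**Working it through.** **Is there a figure to reproduce?** No. The documents give no SD, effect size, power or expected availability for HbA1c. The only figures are 250 per arm and 500 in total, and these agree. Everything below is illustrative.

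**Assumptions.** SD 1.5 HbA1c points. Routine tests at a mean interval of 6 months, irregular (coefficient of variation 0.3 to 0.5). Variance split 60% stable between-person, 30% serial correlation decaying as exp(-lag/9 months), 10% noise. All analyses use values up to T3 only, because Table 2 lists T0 to T3.

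**Single-value analyses.** With a share p of participants having a value:

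- unadjusted SE = 1.5 × √(2/(250p))
- baseline-adjusted SE = unadjusted SE × √(1 − r²), with r = 0.6 + 0.3·exp(−lag/9)

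With 6-monthly tests at a random phase, the last pre-randomization value is on average 3 months old and p = window/6. The lag is taken from that value to the middle of the window.

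| Value used | p | Unadjusted SE | Lag, r | Adjusted SE |
|---|---|---|---|---|
| Within 1 month before T3 | 0.17 | 0.33 | 14.5, 0.66 | 0.25 |
| Within 1.5 months before T3 | 0.25 | 0.27 | 14.25, 0.66 | 0.20 |
| Within 3 months before T3 | 0.50 | 0.19 | 13.5, 0.67 | 0.14 |
| Last value in months 6-12 | 0.81-0.87 (irregular tests) | 0.14-0.15 | 12, 0.68 | 0.105-0.110 |

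For example, the 3-month row is 1.5 × √(2/125) = 0.190, and 0.190 × √(1 − 0.67²) = 0.14.

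**Mixed model.** This is the generalized-least-squares variance of the 12-month arm contrast, using the last pre-randomization value and all dated values to T3, with a common baseline mean:

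- arm effect linear in time: SE 0.128 to 0.131, about 0.13
- effect established by month 3: about 0.085
- quadratic arm effect: 0.156 to 0.163

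**The wide window.** The baseline-adjusted last value in months 6-12 has a smaller SE than the linear mixed model: 0.13/0.108 = 1.20. But at a random phase its average draw time is month 9, so under linear build-up it estimates about 9/12 = 75% of the 12-month effect. Put on the 12-month scale, its SE is 0.105/0.75 to 0.110/0.75, about 0.14 to 0.15.

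**Where the gain comes from.** A separate check used fixed visits at 0, 6 and 12 months, a free mean at each visit, and correlations of 0.5 to 0.8. Adding the 6-month value to a baseline-adjusted 12-month regression lowers the SE by:

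- 0% if all 12-month values are present
- 0.7 to 4.0% if 80% are present
- 1.7 to 10.3% if 50% are present

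Baseline adjustment alone lowers the SE by 1 − √(1 − r²): 20% at r = 0.6, 29% at 0.7 and 40% at 0.8. For most correlations tried, baseline HbA1c contributes more than the earlier follow-up values.

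**The case against.** The strongest reply has five parts.

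- **Missing data are provided for.** The sentence on multiple imputation follows directly, and imputation could draw on earlier HbA1c values and recover about what a mixed model would. A reader might infer that earlier values are discarded, but the documents do not say that. What stands is that the plan does not say they will be used, and imputation needs a window before it is known which values are missing.
- **No availability figure exists.** A reader might infer that many participants will have no usable outcome. The documents give no number, and under the same assumptions the last value in months 6-12 is available for 81 to 87%. The narrow-window figures describe windows that the plan never states. What stands is that nothing rules them out.
- **The gain depends on the effect's shape.** This is correct. The 0.085 rests on an early effect, and with a quadratic arm effect the mixed model is less precise than a baseline-adjusted 3-month window (0.14). With a free mean at fixed visits the gain from earlier follow-up values is 0 to about 10% of the SE. A claim of a large, general loss of precision is not supported.
- **Testing may differ by arm.** The intervention prompts testing, so who has a value, and when, may depend on arm. Neither a mixed model nor imputation removes that unless missingness at random is plausible. This stands, and the fix has to address it.
- **HbA1c is secondary.** This is true, and it limits how much the point matters.

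**Conclusion.** The point holds in a limited form. The reason given for leaving the mixed model does not support the choice. The 12-month value is undefined, and baseline HbA1c is missing from the covariate list. On the assumptions above with linear build-up, the mixed model's SE of about 0.13 compares with 0.14, 0.20 and 0.25 for one baseline-adjusted value within 3, 1.5 and 1 months before T3. Those SEs are about 8%, 54% and 92% larger. In 95% confidence half-widths the range is 1.96 × 0.13 = 0.25 to 1.96 × 0.25 = 0.49 HbA1c points. The plan's default when there is no imbalance, an unadjusted regression, gives 0.14 to 0.15 if it takes the last value in months 6-12. Only that same value with baseline adjustment has a smaller SE (0.105 to 0.110), and it reflects a time earlier than 12 months.

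These sizes rest on an assumed SD, testing interval, correlation and effect shape, none of which the documents give. The conclusion that does not depend on them is that the estimate turns on an unstated window. The primary care-gap analysis is unaffected.

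**What to change.** Replace the HbA1c sentence in section 6.0 with wording such as:

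> HbA1c will be analysed with a linear mixed model using the last pre-randomization value and every dated EHR value through T3, with draw date as continuous time, a common baseline mean in both arms and a prespecified shape for the arm-by-time effect. The estimate reported is the arm difference at 12 months.

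If a cutoff later than T3 is preferred, state it and use it in all HbA1c analyses.

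Keep the single-value linear regression as a sensitivity analysis, with three additions: a stated window and rule for choosing the value, adjustment for baseline HbA1c whether or not there is imbalance, and earlier HbA1c values in the imputation model. Report the number and timing of HbA1c tests by arm, and add a sensitivity analysis for values not missing at random.

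The cost is SAP wording and one different model on data already to be abstracted. The real downside is that an effect shape must be chosen in advance. Against a baseline-adjusted last value in months 6-12, the SE may be about 20% larger under linear build-up, although that value describes an earlier time.

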## **2.0 Rationale and Specific Aims**

In a prior study (IRB # 200241), we designed a patient portal intervention to:

- a) notify patients when selected, clinically meaningful, evidence-based diabetes monitoring & preventative services (eg, annual eye exam) become due and provide reminders for timely completion,
- b) promote understanding of the importance of these services through literacy sensitive content, and
- c) allow patients, when due by evidence-based guidelines, to initiate an order for the care (e.g., pneumococcal vaccination).

Then, in a subsequent study (IRB# 202281), we tested the usability of the patient portal intervention.

In this study, we aim to evaluate the effect of the above patient portal intervention on completion of selected evidence-based, clinically-meaningful, diabetes monitoring & preventative services and secondary intermediate outcomes (e.g., diabetes self-efficacy). We hypothesize that a pragmatic, cluster randomized controlled trial will demonstrate the patient portal intervention described above will increase completion of selected evidence-based, diabetes monitoring & preventative services and secondary intermediate outcomes such as diabetes self-efficacy.

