Patients reporting an outside eye exam will be contacted by study staff and asked to complete an Authorization for Release of Medical Information to VUMC via REDCap. If the patient agrees and signs the release, trained study staff will request the records accordingly. Once the eye exam records are received, trained study staff will review the records to determine if the records document screening for diabetic eye disease (i.e., was the participant's self-report of a diabetes eye exam accurate). If the eye exam records do not indicate screening for diabetes related eye disease (i.e., a diabetes eye exam), KSP will contact the participant by phone with this information and encourage the participant to call their eye doctor to schedule a diabetes eye exam. If the participant prefers, the participant will be invited to schedule a diabetes eye exam at Vanderbilt Eye Institute. If the participant can't be reached by phone, they will be sent a letter with this information. Any outside eye exam records received will be scanned into the participant's VUMC medical record and their primary care physician will be notified.

[Data Collection and Outcome Measures.](#) Study participants will complete questionnaires electronically via email using REDCap™ at four time points: enrollment/baseline (T0), 3-month follow-up (T1), 6-month follow-up (T2), and 12-month

follow-up (T3). Participants will complete an enrollment/baseline questionnaire (T0) including basic demographic questions, items about computer and internet use, health literacy, numeracy, and eHealth literacy. Based on prior experience, we estimate time to completion for each questionnaire to be about 20 minutes. Participants will be compensated \$40 each for completing questionnaires (\$160 total if they complete all four).

The primary outcome measure will be the number of diabetes care gaps out of the four selected DM monitoring & preventative services through 12-months follow-up.

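### The 12-month HbA1c model does not pre-specify baseline HbA1c as a covariate, although the plan abstracts HbA1c from T0; this gives up precision on a secondary outcome

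*Combined protocol and SAP*

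**What the plan says.** Section 6.0 sets HbA1c apart from the other secondary outcomes and fits a regression "with the HbA1c value at the 12-month timepoint as the dependent variable". No covariate is named for this model. The stated reason for treating it separately is: "Due to the frequency of HbA1c measurements, we will use a linear regression model as opposed to a mixed effects model".

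The only covariate rule in the section is conditional: "If there is imbalance, we will control for baseline patient level covariates". The list that follows is open-ended. It names socioeconomic status, marital status, race/ethnicity, education, age, sex, health literacy, technology use and diabetes distress. It does not name HbA1c, or the baseline value of the outcome in general. Whether the rule governs the HbA1c model at all is not stated.

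Table 2 lists HbA1c over T0 to T3, with T0 defined as baseline. The text below the table gives the source: "Additional secondary outcomes, blood glucose control and treatment intensification, will also be assessed by EHR abstraction". On missing data, Section 6.0 says: "Appropriate statistical methods, such as multiple imputation, will be used where missing data are present".

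**The concern.** A patient's earlier HbA1c is likely to be among the best predictors of the later one. A mixed model could use the T0 value as one of the repeated measures. The stand-alone regression has no stated use for it, so data that the plan already collects are left out of the analysis.

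Tying adjustment to observed imbalance does not repair this. Adjusting for a prognostic baseline reduces residual variance whether or not the arms look balanced. A trigger of this kind also leaves the choice of model to be made after the data are seen.

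At stake is the width of the confidence interval for the trial's glycaemic outcome. There is also a smaller, conditional issue about who has a 12-month value. HbA1c is read from the record, follow-up is by emailed questionnaire ("Study participants will complete questionnaires electronically via email"), no study blood draw is described, and only Arm 2 is prompted to test.

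**Working it through.** The documents give no HbA1c standard deviation, correlation or detectable difference, so there is no figure of the plan's own to reproduce.

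**Inputs.** From Section 4.0: 250 per arm. Assumed: correlation ρ between baseline and 12-month HbA1c of 0.5, 0.6 or 0.7; SD 1.5 HbA1c points; share f of patients with a usable baseline, missing at random; complete 12-month values for steps 1 to 4.

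**1. Unadjusted.** SE = SD × √(2/250) = 0.0894 SD. The 95% half-width is 1.96 × 1.5 × 0.0894 = 0.263 points.

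**2. Adjusted, all baselines present.** Relative variance is 1 − ρ².

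| ρ | Relative variance | SE cut | Equivalent extra patients | Half-width |
|---|---|---|---|---|
| 0.5 | 0.75 | 13.4% | 33% | 0.228 |
| 0.6 | 0.64 | 20.0% | 56% | 0.210 |
| 0.7 | 0.51 | 28.6% | 96% | 0.188 |

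The SE cut is 1 − √(relative variance). Equivalent extra patients is 1/(relative variance) − 1.

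**3. Some baselines missing.** The result depends on the method.

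- Missing-indicator term: relative variance is 1 − fρ².
- Multiple imputation of baseline from arm and outcome: large-sample relative variance is (1 − ρ²)(1 − ρ² + ρ²/f).

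| f | ρ | SE cut, indicator | SE cut, multiple imputation |
|---|---|---|---|
| 0.7 | 0.5 | 9.2% | 8.9% |
| 0.7 | 0.6 | 13.5% | 14.0% |
| 0.7 | 0.7 | 18.9% | 21.4% |
| 0.5 | 0.5 | 6.5% | 3.2% |
| 0.5 | 0.6 | 9.4% | 6.7% |
| 0.5 | 0.7 | 13.1% | 12.8% |

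At f = 0.5 the indicator method is worth 14% to 32% more patients (1/0.875 − 1 to 1/0.755 − 1). Setting the imputation formula equal to 1 gives f = (1 − ρ²)/(2 − ρ²). At ρ = 0.5 that is 0.75/1.75 = 0.43, so with fewer than about 43% of baselines available imputation gains nothing. The indicator method never loses precision on these formulas.

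**4. Why a trigger is a poor rule.** A chance baseline difference at its 95% limit is 1.96 × 0.0894 = 0.175 SD. Carried forward, it moves the unadjusted 12-month difference by 0.5 × 0.175 = 0.088 SD to 0.7 × 0.175 = 0.123 SD. That is about one standard error or more.

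**5. Limit of the remedy if testing differs by arm.** This is an illustration and does not follow from the written plan. Assume no true effect, that only tested patients are analysed, and that prompted testers are a random sample of those otherwise untested. The bias is then (pT − pC)/pT × gap, where pT and pC are the proportions tested in the intervention and usual-care arms and gap is the HbA1c difference between patients tested anyway and those otherwise untested.

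- Mild case: 85% v 80% tested, gap 0.3. Bias is 0.05/0.85 × 0.3 = 0.018 points and the false-positive rate is 5.2%.
- Harsh case: 80% v 60% tested, gap 0.8. Bias is 0.20/0.80 × 0.8 = 0.20 points. SE is 1.5 × √(1/150 + 1/200) = 0.162, and the false-positive rate is about 23.5%.

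If testing in the harsh case depends only on the 12-month value, adjusting at ρ = 0.6 leaves the bias at 0.20 and shrinks the SE to 0.8 × 0.162 = 0.130. The false-positive rate then rises to about 34% on this approximation. A simulation with multiple imputation on arm and a fully observed baseline gave 32%.

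**The case against.** The case for leaving the plan alone is fair in several respects. Randomisation makes the unadjusted comparison unbiased when HbA1c data are complete. HbA1c is secondary. The covariate list is open, so baseline HbA1c could be added. Modelling a single time point is a reasonable response to irregular testing, and nothing here faults that choice. These arguments limit the point to precision and pre-specification. They do not remove it, because adding the term only after imbalance is seen is not pre-specification.

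The gain is also smaller than the full-baseline figures suggest. Section 5.0 recruits partly from a report of patients with care gaps, and one gap in Table 2 is "no hemoglobin A1C blood test in the last 6 months". Some patients will therefore lack a recent baseline. That objection stands, and it is why step 3 gives ranges by availability and method.

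A reader might infer more: that the HbA1c result will be biased because the intervention prompts testing. Section 2.0 does expect that "the patient portal intervention described above will increase completion of selected evidence-based, diabetes monitoring & preventative services", and HbA1c testing is one of those services. The documents do not support a finding of bias, however. The plan does not say that only tested patients will be analysed. It mentions multiple imputation without stating the model, and it gives no testing rates. Part of recruitment is through upcoming appointments, which may prompt testing in both arms. The mild case in step 5 is almost harmless, and the direction of any bias is unknown. What stands is a short caveat.

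**Conclusion.** The point holds as a loss of precision and a gap in pre-specification for one secondary outcome. It is not a finding of bias, and it does not touch the primary analysis.

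Under the assumed correlations of 0.5 to 0.7, the written analysis forgoes an SE reduction of 13–29% if all baselines are usable. With half usable it forgoes about 6.5–13% with a missing-indicator term, or about 3–13% with multiple imputation. These sizes rest on the assumed correlation and on baselines missing at random. An old baseline value would probably correlate less and earn less.

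Adjustment would not cure selective testing that depends on the unobserved 12-month value. By shrinking the SE around an unchanged bias, it could raise the false-positive rate in that situation. The change is worth making as a cheap improvement.

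**What to change.** In Section 6.0:

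- Always adjust the HbA1c model for the most recent pre-randomisation HbA1c within a stated look-back window, whatever the observed imbalance.
- Handle a missing baseline with a missing-indicator term, or a single imputation made without reference to arm.
- State the window that defines the 12-month value.
- If 12-month values are multiply imputed, include arm, baseline HbA1c and interim HbA1c in the imputation model.
- Report the proportion tested in each arm beside the result. State that adjustment does not remove bias, and can raise the false-positive rate, if testing depends on the unobserved 12-month value.

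The cost is one or two sentences of SAP text for the adjustment itself, a short addition for the windows and reporting, and a little analysis work. Table 2 already plans abstraction from T0, so no new data collection is needed. The downside is that the gain shrinks as more patients lack a recent baseline.
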